► **IF YES, provide a justification for the use of a placebo**

Answer/Response: N/A

Human Participants

Ages: 18-100

Sex: Men and women

Race: All

Subjects- see below

1. Provide target # of subjects (at all sites) needed to complete protocol.

Answer/Response: 100

2. Describe expected rate of screen failure/ dropouts/withdrawals from all sites.

Answer/Response: 20

3. How many subjects will be enrolled at all sites?

Answer/Response: 120

4. How many subjects will sign a consent form under this UVa protocol?

Answer/Response: 120

Inclusion/Exclusion Criteria

1. List the criteria for inclusion

Answer/Response:

- age \geq 18 years,
- diagnosis of cirrhosis,
- admission to hospital

2. List the criteria for exclusion

Answer/Response:

- age $<$ 18 years,
- prior enrollment in study (i.e. readmission),
- prisoner,
- prednisone or hydrocortisone use in the past 24 hours,
- pregnancy

3. List any restrictions on use of other drugs or treatments.

Answer/Response: None

Statistical Considerations

1. Is stratification/randomization involved?

Answer/Response: No

► IF YES, describe the stratification/ randomization scheme.

Answer/Response: N/A

► IF YES, who will generate the randomization scheme?

 Sponsor

UVa Statistician. Answer/Response:
UVa Investigational Drug Service (IDS)
Other: Answer/Response:

2. What are the statistical considerations for the protocol?

Answer/Response:

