Subjects will be classified as adrenally sufficient or insufficient on the basis of standard-dose cortisol stimulation test. Variables of interest for comparison between the groups include MELD score, Child-Turcotte-Pugh (CTP) classification, high-density lipoprotein (HDL) levels, presence of spur cell anemia, serum cholesterol ester percentage (surrogate for LCAT enzymatic activity), cortisol binding globulin levels, and free cortisol levels. Student's t-test and Chi Square tests will be utilized to determine significance; a p-value <0.05 will be used as our threshold for significance. If multiple factors are found to be significantly different in a univariate fashion between classification groups, a multivariate logistic regression analysis will be performed for adjusted analysis. We will also seek to define any correlations between variables. Furthermore, we will assess correlation between MELD score and serum cholesterol ester percentage, spur cell anemia, HDL levels, cortisol binding globulin levels, and free cortisol levels; similar correlate analysis will be done using CTP classification instead of MELD score.

Prevalence of adrenal insufficiency (AI) in cirrhosis varies widely based on several factors, including severity of liver disease (i.e. MELD score or CTP classification) and the testing modality used to assess for AI. Given that admitted patients to UVA are typically CTP B or C, we expect the incidence to be about 33%. Thus, 120 patients recruited should be sufficient to provide a statistical difference in our outcome measures of interest, assuming a 20% dropout rate to lead to 100 patients completing study protocol.

3. Provide a justification for the sample size used in this protocol.

Answer/Response:

Given that admitted patients to UVA are typically CTP B or C, we expect the incidence of adrenal insufficiency to be about 33%. We feel 100 patients would be adequate to complete a pilot study to test for correlation between adrenal insufficiency, low serum cholesterol ester percentage, and spur cell anemia. There is no current literature upon which to do a formal power calculation (although low levels of cholesterol esterification is a well-established near-universal metabolic finding in cirrhotic patients), but this sample size would allow for adequate size comparator groups and decrease the likelihood of a Type II statistical error.

4. What is your plan for primary variable analysis?

Answer/Response:

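### The sample-size figures in item 2 (120 recruited, 20% dropout, 100 completers) do not agree, and its sufficiency claim goes further than item 3 supports; minor, fixed by wording

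*Combined protocol and SAP*

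**What the plan says.** Three places bear on sample size.

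- **Human Participants, items 1 to 4.** The target to complete is 100. Asked for the "expected rate of screen failure/ dropouts/withdrawals from all sites", the plan answers 20, with no unit. Both the number enrolled and the number signing consent are 120.
- **Statistical Considerations, item 2.** About 33% of patients are expected to have adrenal insufficiency (AI). From this the plan concludes that "120 patients recruited should be sufficient to provide a statistical difference in our outcome measures of interest". The same sentence then gives the allowance for losses behind that number: "assuming a 20% dropout rate to lead to 100 patients completing study protocol". The same item warns that "Prevalence of adrenal insufficiency (AI) in cirrhosis varies widely based on several factors". It sets the threshold at p < 0.05 and says that Student's t-test and "Chi Square tests will be utilized to determine significance".
- **Statistical Considerations, item 3.** "We feel 100 patients would be adequate to complete a pilot study to test for correlation between adrenal insufficiency", low cholesterol ester percentage and spur cell anemia. The plan adds: "There is no current literature upon which to do a formal power calculation". It also says that the number gives comparator groups of adequate size and makes a Type II error less likely.

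Item 4 names the primary outcome as two prevalences, cholesterol esterification deficiency and spur cell anemia, compared between patients with and without AI. The continuous measure, "serum cholesterol ester percentage (surrogate for LCAT enzymatic activity"), is among the comparison variables in item 2 but is not the primary outcome as item 4 words it.

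**The concern.** There are two separate problems.

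First, a dropout rate is normally a fraction of those recruited. Read that way, item 2's rate does not take 120 to 100. The number of evaluable patients is the denominator of every planned comparison, so it should be stated once and follow from its inputs. The 20 in Human Participants does not settle the matter: the form asks for a rate and the answer carries no unit. As a count it fits the figures around it; as a percentage of 120 it does not.

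Second, item 2 moves from an expected 33% split straight to sufficiency for a statistical difference. A split fixes group sizes. Power also needs a difference to detect and either a standard deviation or event rates, and the plan gives none of these. Item 3 says that no formal calculation could be made, so item 2 asserts something item 3 does not support. A non-significant result could then be read as evidence of no association, on the strength of a sufficiency that was never calculated.

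**Working it through.** **Inputs from the plan.** Recruited 120; dropout 20%; completers 100 (Statistical Considerations, item 2). Target 100, losses 20 without a unit, enrolled 120, consented 120 (Human Participants). Expected AI 33%; threshold p < 0.05 (item 2).

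**Step 1: the plan's own figure, taken as stated.**
- Completers from 120 at 20% loss: 120 × (1 − 0.20) = 96, which is 4 below the stated 100.
- Recruits needed for 100 completers at 20% loss: 100 / (1 − 0.20) = 125, which is 5 above the stated 120.
- Loss implied by 120 and 100: (120 − 100) / 120 = 20 / 120 = 16.7%.

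**Step 2: what does reproduce 120.**
- Adding 20% of the completers: 100 × 1.20 = 120.
- Reading the 20 in Human Participants as subjects: 100 + 20 = 120.

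Either could be the origin of the figure. Neither is a 20% dropout rate among those recruited. Study Procedures, item 1, places the pregnancy test after consent, so losses at that step also come out of the 120.

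**Step 3: effect on precision.** Group sizes are 0.33 × 100 = 33 (33 vs 67), or 0.33 × 96 = 31.7, about 32 (32 vs 64). Assumptions, because the plan gives neither: 80% power and a two-sided test at 0.05. The normal approximation to the detectable mean difference in SD units is (1.960 + 0.842) × √(1/n₁ + 1/n₂).
- 33 vs 67: 2.802 × 0.2127 = 0.596.
- 32 vs 64: 2.802 × 0.2165 = 0.607.

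The t distribution gives slightly larger values:

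| Evaluable | Split | Detectable difference (t-test) |
|---|---|---|
| 100 | 33 / 67 | 0.602 SD |
| 96 | 32 / 64 | 0.613 SD |

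The difference is about 0.01 SD.

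**Step 4: what the sample could detect on prevalences, the form of the primary outcome.** Same power and level, uncorrected chi-square, no adjustment for two primary comparisons, power by exact enumeration of the two binomials. The non-AI prevalences are assumed, since the plan gives none.

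| Assumed prevalence without AI | Prevalence with AI detectable at 33 / 67 | At 32 / 64 |
|---|---|---|
| 10% | 33.0% | 33.2% |
| 30% | 59.2% | 59.6% |

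So 100 evaluable patients can detect differences of roughly 23 to 29 percentage points under these assumptions. Whether that is sufficient depends on the difference the investigators care about, which the plan does not state.

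**The case against.** The strongest reply is that nothing operational depends on this. Read as counts, Human Participants is consistent: 100 complete, 20 are lost, 120 are enrolled. The only wrong token is then the percent sign in item 2. Item 3, which answers the form's sample-size question and follows directly after item 2, openly calls the study a pilot and says that no formal power calculation was possible. Item 2 is itself hedged, and a pilot does not have to be powered. Most of this stands, and it is why the point is minor. It does not remove the inconsistency within one sentence of item 2, and it does not make item 2's conclusion follow from a split alone.

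Three stronger readings are tempting, and the documents do not support them.

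- **A reader might infer that 100 patients are too few.** The plan states no target difference, so insufficiency is no more demonstrated than sufficiency.
- **A reader might infer that 125 must be enrolled.** That would also make the figures agree, but the gain in precision is negligible, and the existing 120 is consistent with 16.7% loss or with 96 evaluable.
- **A reader might infer that the esterification prevalence comparison cannot succeed**, because item 3 calls low cholesterol esterification nearly universal in cirrhosis. That depends on a cutoff for deficiency, which the plan does not define, and on assumed rates. The Objectives section describes the enzyme as deficient in only some cirrhotic patients.

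**Conclusion.** Wrong as written, but minor. With dropout taken as a share of those recruited, 120, 20% and 100 are incompatible: the shortfall is 4 completers or 5 recruits, or the rate should read 16.7%. That conclusion is arithmetic on the plan's own figures. The consequence is about 0.01 SD in detectable difference (0.60 against 0.61 SD), assuming 80% power, a two-sided 0.05 level and the plan's 33% AI.

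Item 2's sufficiency statement has no effect size, rates or power behind it and goes beyond item 3. Item 3's disclosure limits the harm to one overconfident sentence. The illustrative prevalences rest on assumed rates and on the 33% split; item 2 itself says that AI prevalence varies widely, and with fewer AI patients the detectable difference would be larger.

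**What to change.** 1. In Human Participants, item 2, write 20 subjects instead of 20.
2. In Statistical Considerations, item 2, write 120 enrolled, 20 lost (16.7%), 100 evaluable. If the investigators really expect 20% of those enrolled to be lost, state 96 evaluable in both sections instead; the completion target and the count of losses in Human Participants then change to 96 and 24.
3. Replace item 2's sufficiency sentence with wording that agrees with item 3, for example:

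> This is a pilot study without a formal power calculation. If about 33 of 100 evaluable patients have AI, then at 80% power and two-sided 0.05 (uncorrected chi-square, no adjustment for two primary comparisons) a prevalence of, for example, 10% vs 33% or 30% vs 59% (non-AI vs AI) is detectable. For the continuous cholesterol ester percentage, which is not the primary prevalence comparison, about 0.6 SD is detectable by t-test. These rates are assumptions.

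If the 96 option is chosen, use 32 of 96 in that text; the examples move by less than one percentage point.

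The cost is wording only. Enrolment stays at 120, and procedures and planned analyses do not change. The plan gives up one unsupported sentence.

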Our primary outcome of interest is comparing prevalence of cholesterol esterification deficiency and spur cell anemia in cirrhotic patients with and without adrenal insufficiency.

5. What is your plan for secondary variable analysis?

Answer/Response:

- Demonstrate association between deficiency in cholesterol esterification and presence of spur cell anemia

- Demonstrate association between deficiency in cholesterol esterification and low HDL levels
- Correlate higher MELD score with presence of adrenal insufficiency
- Correlate higher MELD score with presence of spur cell anemia
- Correlate higher MELD score with lower HDL levels
- Correlate higher MELD score with deficiency in cholesterol esterification
- Correlate higher CTP classification with presence of adrenal insufficiency
- Correlate higher CTP classification with presence of spur cell anemia
- Correlate higher CTP classification with lower HDL levels
- Correlate higher CTP classification with deficiency in cholesterol esterification
- Correlate lower cortisol binding globulin levels with higher MELD score and CTP classification
- Correlate lower cortisol binding globulin levels with adrenal insufficiency
- Correlate lower free cortisol levels with higher MELD score and CTP classification
- Correlate lower free cortisol levels with adrenal insufficiency
- Multivariate logistic regression if several variables are found to be significant

6. Have you been working with a statistician in designing this protocol?

Answer/Response: No

IF YES, what is their name?

Answer/Response: N/A

7. Will data from multiple sites be combined during analysis?

Answer/Response: No

7(a). Does the study involve randomization?

Answer/Response: No

IF YES, will randomization be done at each site or among sites?

Answer/Response: N/A

7(b). Has the sample size calculation considered the variation among sites?

Answer/Response: N/A

7(c). When combining the data from multiple sites to assess the study results, is the effect of the treatment to be tested (or the association to be tested) assumed to be the same across sites or vary among sites? What is the modelling strategy?

Answer/Response: N/A

7(d). Is there a common protocol used in all sites?

Answer/Response: N/A

IF NO, how will differences among sites, such as those related to the implementation, inclusion criteria, patient characteristics, or other sites characteristics, be considered to assess the study results?

Answer/Response: N/A

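### The esterification half of the primary outcome is a yes/no deficiency with no cut-off; the ester percentage, already measured, should be the primary measure

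*Combined protocol and SAP*

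**What the plan says.** All references are to the combined protocol and SAP.

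- **Statistical Considerations, item 4 (primary):** "Our primary outcome of interest is comparing prevalence of cholesterol esterification deficiency and spur cell anemia in cirrhotic patients with and without adrenal insufficiency". No test is named and deficiency is not defined.
- **Item 2:** the serum cholesterol ester percentage is one of the variables to be compared between patients with and without AI. On correlations, "we will assess correlation between MELD score and serum cholesterol ester percentage" and several other variables, with the same to be repeated for CTP class. The t-test and the chi-square test are both named, at p<0.05, without saying which variable gets which.
- **Item 3 (sample size):** the aim is to "test for correlation between adrenal insufficiency, low serum cholesterol ester percentage, and spur cell anemia". The same item remarks that "low levels of cholesterol esterification is a well-established near-universal metabolic finding in cirrhotic patients".
- **Item 5 (secondary):** four bullets use deficiency in esterification, against spur cells, HDL, MELD and CTP. One example is "Correlate higher MELD score with deficiency in cholesterol esterification".
- **Study Procedures, item 1:** serum cholesterol esters are among the laboratory tests for eligible subjects.

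No threshold, reference range or source for deficiency appears anywhere in the document.

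**The concern.** The plan carries two versions of one variable: a measured percentage in item 2 and an undefined yes/no state in items 4 and 5. It makes the undefined one primary. Two things follow.

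First, the cut-off is open. One chosen after looking at the data could decide the primary result, and nothing in the plan prevents that. This is the main point and it needs no assumed effect size.

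Second, every patient has cirrhosis, and the plan itself describes low esterification as nearly universal in cirrhosis. If the eventual cut-off tracks that description, almost everyone in both groups will be deficient. The comparison then says nothing, even if the ester percentage really differs.

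The spur cell half of the primary outcome is not at issue here.

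**Working it through.** **Inputs.** From item 2: 100 completers, about 33% with AI (so 33 versus 67) and a 0.05 threshold. Two-sided testing is assumed because sidedness is not stated. The chi-square test is inferred from the word prevalence together with item 2 ("Chi Square tests will be utilized to determine significance"). The plan gives no power, effect size, SD or deficiency rate, so it offers no power figure to reproduce.

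**1. Cut-off chosen afterwards, no true difference.** Uncorrected Pearson chi-square, 33 versus 67. This holds for any continuous distribution. The ranges for three and five cut-offs are from separate simulation runs.

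| Cut-offs tried (% of patients deficient) | p<0.05, either direction | p<0.05, AI group worse |
|---|---|---|
| one fixed (50, 80 or 90) | 4.3–4.8% | 1.5–2.4% |
| best of three (70, 80, 90) | 10.4–10.6% | 4.3–4.5% |
| best of five (50, 60, 70, 80, 90) | 14.8–15.0% | 6.6–6.8% |

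**2. Ceiling.** Let m be the number with AI and k the number of non-deficient patients among 100. The most favourable table in the expected direction puts all k in the non-AI group. The statistic is then

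X² = 100·m·k / [(100 − m)(100 − k)], to be compared with 3.84.

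- m = 33, k = 7: 100·33·7 / (67·93) = 23,100 / 6,231 = 3.71, p = 0.054.
- m = 33, k = 8: 100·33·8 / (67·92) = 26,400 / 6,164 = 4.28, p = 0.038 (Fisher 0.0498).

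So with more than 92 of 100 deficient, significance in the expected direction is impossible. The plan says "Prevalence of adrenal insufficiency (AI) in cirrhosis varies widely based on several factors", so the AI count was varied:

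| Patients with AI | 20 | 25 | 30 | 33 | 40 | 50 |
|---|---|---|---|---|---|---|
| Largest number deficient that still allows p<0.05 | 86 | 89 | 91 | 92 | 94 | 96 |

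**3. Power, as a secondary argument.** Assume normal percentages with equal SD and the AI group 0.6 SD lower; this figure is not in the document. The t-test noncentrality is 0.6 / √(1/33 + 1/67) = 0.6 / 0.2127 = 2.82 on 98 degrees of freedom. That gives 80% power for Student and 79% for Welch. The chi-square test, by exact binomial enumeration, gives:

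| Deficient overall | 50% | 80% | 90% | 95% |
|---|---|---|---|---|
| Chi-square power | 60% | 41% | 22% | 4% |

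The ranking depends on the shape of the distribution:

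| Assumed model | Welch | Chi-square |
|---|---|---|
| Right-skewed gamma, 0.6 SD shift, 80% deficient | 77–78% | 21–27% |
| Left-skewed gamma, 0.6 SD shift, 80% deficient | 81–83% | 78–100% |
| 20% of non-AI patients 3 SD higher, 82–87% deficient | 64% | 59–70% |
| 25% of non-AI patients 3 SD higher, 79–84% deficient | 80% | 76–86% |

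At 95% deficient, chi-square power was at most 13% in every shift model tried.

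**4. Why Welch.** If the AI group's SD is 1.5 times larger (assumed), Student's type I error is 8.5–8.7%, against 5.0–5.1% for Welch.

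**The case against.** The defect is a missing cut-off, and writing one into item 4 would cure it. Replacing the investigators' prevalence with a mean difference goes further, and power does not settle the matter: under left skew or a preserved subgroup, a well-placed cut-off can match or beat the t-test. The ceiling is not established either. The plan says low levels are nearly universal, which is not the same as saying deficiency is, and a cut-off set within the cirrhotic range would avoid the problem. Item 2 already lists the percentage for the group comparison and for correlation with MELD and CTP. The study is called a pilot, and in the hypothesised direction the inflation is to roughly 4.5–7%, not 10–15%.

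Much of this stands. The ceiling is conditional, the power ranking depends on the model, and a cut-off fixed beforehand is an acceptable minimum. But a well-placed cut-off helps only if it is placed in advance, and none is. Item 2 does not make the percentage primary or assign it a test. The pilot label does not remove the stated p<0.05 threshold. The inflation figures show what the plan permits, not what anyone intends.

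One limit also stands: the document gives no cortisol cut-off for AI itself, so this change closes one open definition in the primary comparison, not all of them.

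**Conclusion.** The concern holds as an inexpensive improvement. That the primary esterification outcome is undefined, while a continuous measure of the same thing is already collected and listed, follows from the text alone. Leaving the cut-off open can raise the false-positive rate from just under 5% to about 10.5–15% if the best of three to five cut-offs is reported. That assumes a 33/67 split and those particular sets of cut-offs. The ceiling at 92 of 100 is exact for that split but matters only if the chosen cut-off labels nearly everyone deficient. The power figures rest on assumed effect sizes and shapes and are supporting evidence only. Confidence is medium, because the document gives no deficiency rate, SD or distribution for the ester percentage.

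**What to change.** - **Item 4:** name the continuous serum cholesterol ester percentage as the primary esterification measure. Compare it between AI and non-AI patients with Welch's t-test and report the mean difference with its 95% CI. With 33 versus 67 patients the half-width is about 0.42 SD (1.98 × 0.2127).
- **Prevalence of deficiency:** report it descriptively by group, against a cut-off and source written into the plan before any ester result is seen. If prevalence must remain primary, putting that cut-off and source in item 4 is the minimum.
- **Item 5:** use the percentage in the four bullets on spur cells, HDL, MELD and CTP. The MELD and CTP bullets then match item 2.
- **Spur cell anemia:** keep it as a proportion.

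The cost is one edit to item 4 and four to item 5. It replaces a primary measure, so it is more than rewording, but it needs no new patient, sample or assay. Two things are given up. A mean difference is less direct to read clinically than a prevalence. A well-chosen cut-off could also have more power if esterification is preserved only in a subgroup or is strongly left-skewed.

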University of Virginia

Is adrenal insufficiency under- diagnosed in hospitalized cirrhosis patients?

NCT03368066

PI: [name]
11-20-2017

PROTOCOL

Background

1. Provide the scientific background, rationale and relevance of this project.

Answer/Response:

Cirrhosis is known to cause various end-organ dysfunction, most notably the hepatorenal and hepatopulmonary syndromes. However, the increased recognition of adrenal insufficiency in cirrhotic patients has led to postulation about the presence of a so-called “heptoadrenal syndrome¹.” While originally this syndrome was recognized in cirrhotic patients with sepsis and shock states^{1,2}, further investigation has also identified adrenal insufficiency in cirrhotic patients with variceal bleeding³ as well as stable patients⁴. Although there is controversy about the best diagnostic test to assess adrenal insufficiency in cirrhotic patients^{5,6}, it is well established that cirrhotic patients with adrenal insufficiency have increased mortality, particularly as they become more decompensated⁷.

In addition to this endocrinological complication, cirrhosis also has a profound effect on a patient’s hematologic parameters. In a study of rheologic properties of 38 patients (18 cirrhotic – mostly of cryptogenic origin, 20 control), cirrhotic patients were noted to have increased erythrocyte rigidity and decreased plasma and blood viscosity⁸. The authors argued that their findings were related to a deficiency of high-density lipoprotein (HDL), although the correlation was admittedly weak in their study. A follow-up study by the same authors also confirmed an increase in erythrocyte rigidity in patients with alcoholic and post-hepatic cirrhosis; importantly, they noted the prior association between alcoholic liver disease and development of macrocytosis as a function of lecithin-cholesterol acetyltransferase (LCAT) enzyme deficiency⁹. This enzyme is responsible for esterification of cholesterol and subsequent incorporation into normal red cell membranes. Interestingly, its deficiency is directly manifested as an altered free cholesterol to phospholipid ratio¹⁰, with the increased cholesterol fraction causing the membrane rigidity previously described.

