Another abnormality well documented in cirrhotic patients, more frequently in patients with advanced disease, is spur cell anemia. Although first described in alcoholic cirrhosis, it is seen in all etiologies and is a poor prognostic marker. A spur cell burden of $\geq 5\%$ was found to be associated with a 67% 90-day mortality rate in a recent study¹¹. Furthermore, patients with spur cell anemia have decreased red blood cell (RBC) lifespan and are transfusion resistant as transfused RBCs quickly acquire the pathologic morphology. Spur cells are thought to occur secondary to red cell membrane abnormalities secondary to altered cholesterol composition, similar to the abnormal erythrocyte rigidity rheologic property described above. Interestingly, the lecithin-cholesterol acetyltransferase enzyme has been investigated as a potential key factor in spur cell anemia. A 1972 study by Cooper et al¹² measured LCAT enzyme activity by way of a surrogate method involving change in serum free cholesterol after 6-hour incubation. Lower levels of LCAT were found in patients with spur cells compared to normal controls; however, there was only a weak association with red cell lipid content.

Furthermore, platelet dysfunction in cirrhosis has also been tied to lipid abnormalities. A review of dyslipidemia in liver disease by Miller noted that platelets, similar to erythrocytes, have an imbalanced cholesterol to phospholipid ratio and associated impaired aggregation¹³. Thus, the deficient primary hemostasis noted in cirrhotic patients may not be just a function of

thrombocytopenia itself but also an intrinsic abnormality of platelet function related to a disruption in normal cholesterol pathways.

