It has been demonstrated that LCAT is a key enzyme for many homeostatic functions within the human body and its deficient production in cirrhosis appears to correlate with various hematologic abnormalities. However, it may very well also play an important role in adrenal steroidogenesis and help explain the so called "hepatoadrenal" syndrome that has begun to permeate through the literature. More importantly, however, is that cholesterol esterification levels, a surrogate marker of LCAT enzymatic activity, are directly associated with mortality and thus can serve as a prognostic indicator. A recent study by Kaiser et al.¹⁴ found that the cholesterol esterification fraction was more accurate than INR for estimation of liver synthetic capability and both 3-month and 1-year mortality. Thus, if one can quantify this deficiency in cirrhotic patients and demonstrate association with several related pathologic conditions, it may soon become a useful biomarker to direct treatment and more reliably predict mortality.

Objectives/Hypothesis

Answer/Response:

The hepatoadrenal syndrome has been well described in the literature and is known to be associated with poorer outcomes in both stable and critically ill cirrhotic patients. In chronic liver disease, adrenal (and more specifically cortisol) insufficiency is thought to be a byproduct of altered lipid metabolism that results in decreased HDL production and thus decreased delivery of cholesterol to the adrenal for subsequent corticosteroid production. Studies to date have implicated lecithin-cholesterol acetyltransferase (LCAT) as the key enzyme which is deficient in some cirrhotic patients, leading to an impaired ability to esterify cholesterol and thus a loss of normal cellular functioning and membrane stability. We seek to quantify this LCAT deficiency in a cohort of cirrhotic patients and demonstrate its association with various abnormal physiologies associated with chronic liver disease, including spur cell anemia, low HDL levels, and adrenal insufficiency.

Study Design: Biomedical

1. Will controls be used?

Answer/Response: No a priori controls (i.e. we will not be including patients without cirrhosis in our study). We will compare cirrhotic patients with and without adrenal insufficiency.

► **IF YES, explain the kind of controls to be used.**

Answer/Response: N/A

2. What is the study design?

Answer/Response: prospective cohort study

3. Does the study involve a placebo?

Answer/Response: No

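### No adjusted analysis is specified for esterification with spur cells or with HDL, although the plan expects liver disease severity to track all three variables

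*Combined protocol and SAP*

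**What the plan says.** The Objectives/Hypothesis section proposes to quantify LCAT deficiency and show its association with several abnormalities, "including spur cell anemia, low HDL levels, and adrenal insufficiency". It gives the enzyme deficiency a causal role in disturbed cell function and membrane stability.

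Statistical Considerations item 2 defines the comparison groups: "Subjects will be classified as adrenally sufficient or insufficient on the basis of standard-dose cortisol stimulation test". It then describes one adjusted analysis: "If multiple factors are found to be significantly different in a univariate fashion between classification groups, a multivariate logistic regression analysis will be performed". The tests named are the t-test and chi-square at p<0.05.

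Item 5 lists the secondary aims. The first two are "Demonstrate association between deficiency in cholesterol esterification and presence of spur cell anemia" and "Demonstrate association between deficiency in cholesterol esterification and low HDL levels". Neither names a covariate. Later entries expect higher MELD, and separately higher CTP, to go with deficient esterification, spur cells and lower HDL. The list ends with "Multivariate logistic regression if several variables are found to be significant", which names no outcome and no covariates.

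Aetiology appears only in the Background. One sentence there cites a "prior association between alcoholic liver disease and development of macrocytosis as a function of lecithin-cholesterol acetyltransferase (LCAT) enzyme deficiency". Of spur cell anemia the Background says: "Although first described in alcoholic cirrhosis, it is seen in all etiologies and is a poor prognostic marker". Aetiology is not in the eligibility criteria, the variables listed in item 2 or the Study Procedures.

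**The concern.** Two of the three associations in the objective have no adjusted analysis, and the plan itself supplies a common cause for both. If sicker patients have lower ester percentage, more spur cells and lower HDL, as item 5 expects, then ester percentage will be associated with spur cells and with HDL even if it affects neither. MELD and CTP are collected, but they are never named as adjusters for these two aims.

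What is at stake is interpretation. The Objectives give LCAT deficiency a mechanistic role, and the Background looks ahead to a biomarker that could guide treatment. A crude association that only restates severity supports neither the mechanism nor information beyond MELD, yet it would be reported as a demonstrated association.

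**Working it through.** **Inputs from the documents.** 100 completers; threshold p<0.05 (taken as two-sided, since sidedness is not stated); MELD expected to track esterification, spur cells and HDL. The plan gives no effect size, correlation or power for these aims, so there is no figure of its own to reproduce. Every strength of relation below is an assumption.

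**Ester percentage and HDL, severity as the only link.** If each correlates ρ with MELD and they are otherwise unrelated, their crude correlation is r = ρ × ρ. The chance of p<0.05 follows from Fisher's z: atanh(r) × √(n − 3), with √97 = 9.849, compared with 1.96.

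| ρ with MELD | r | atanh(r) × 9.849 | Chance of p<0.05 |
|---|---|---|---|
| 0.3 | 0.09 | 0.889 | 14% |
| 0.4 | 0.16 | 1.589 | 36% |
| 0.5 | 0.25 | 2.516 | 71% |

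The MELD-adjusted (partial) correlation is (r − ρ²)/(1 − ρ²). This is 0 in every row, because r = ρ².

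**Both aims by simulation.** 3,000 studies of 100 patients per scenario, no direct effect of esterification, spur-cell prevalence assumed 15% or 30% (ranges span the two). Adjusted models were ordinary logistic (spur cells) and linear (HDL) regression on ester percentage plus severity.

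| Severity assumption | Spur cells, crude | HDL, crude | Either, severity-adjusted |
|---|---|---|---|
| no common cause | 5% | 5% | 5% |
| correlation 0.3; spur-cell OR 1.5 per SD | 7–9% | 14–15% | 4–5% |
| correlation 0.5; spur-cell OR 2 per SD | 21–33% | 70–71% | 4–5% |

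**Alcohol aetiology, spur cells.** Assume 40–50% alcohol-related, spur cells 20–40% v 10%, deficiency 60–70% v 40%, and no link within strata.
- Top of the range (40% alcohol-related, spur cells 40% v 10%, deficiency 70% v 40%): both = 0.4×0.28 + 0.6×0.04 = 0.136; spur only = 0.22 − 0.136 = 0.084; deficient only = 0.52 − 0.136 = 0.384; neither = 0.396. Crude OR = (0.136 × 0.396)/(0.084 × 0.384) = 1.67.
- Bottom of the range (50%, 20% v 10%, 60% v 40%): (0.08 × 0.43)/(0.07 × 0.42) = 1.17.
- The uncorrected chi-square test gives p<0.05 in 6–18% of studies across this range.
- Item 3 of Statistical Considerations calls low esterification nearly universal in cirrhosis. With deficiency set instead at 95% v 85–90%, the figure is 2–4%, so there is no inflation.
- With continuous ester percentage and half the patients alcohol-related, it is 7–9% (spur-cell OR 3, ester percentage 0.5 SD lower) or 14–23% (OR 5, 0.8 SD lower).

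**Alcohol aetiology, HDL.** In those last two scenarios the crude HDL test stays at about 5%. It rises to 14–15% (under the stronger one) only if alcohol is also assumed to lower HDL by 0.5 SD, an effect the documents do not mention.

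**Events for the spur-cell model.** At an assumed prevalence of 10–30%, 100 patients give 10–30 events: 5–15 per term with two terms, 3.3–10 with three.

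**The case against.** The strongest reply is that association is the stated aim. A correlation that arises through severity is a real marginal association, so the 14–71% is power to detect it. It is an error rate only if the result is read as a direct link. This stands, and the crude result should be kept. What remains is that the Objectives go beyond description and give LCAT deficiency a mechanism.

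A second reply is that esterification itself reflects liver synthetic function, so conditioning on MELD may remove part of what is being measured. This also stands. It is why the adjusted estimate should sit beside the crude one and not replace it.

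Third, the plan already reports MELD correlations and seeks correlations among variables in general. If all three are Pearson coefficients in the same patients, a reader could derive the ester-HDL partial correlation. That is partial cover only: no coefficient is named, and nothing similar serves a binary spur-cell outcome.

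Some stronger readings are tempting but not supported:
- *Alcohol explains both associations.* The documents never link alcohol to HDL. Even for spur cells the evidence is thin: the LCAT sentence concerns macrocytosis, and the spur-cell sentence says that all aetiologies are affected.
- *The regression certainly has AI as its outcome.* Item 2 implies this through its reference to the classification groups, but the closing entry of item 5 names no outcome. It is safer to say that no adjusted model is specified for these two aims.
- *Aetiology will be lost.* The list in item 2 is not a data-collection form, and the electronic record is available. Recording aetiology at enrolment is simply tidier.

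**Conclusion.** The point holds as a gap in specification with a consequence for interpretation. Severity is the one common cause that the plan itself supports for both associations. Under assumed correlations of 0.3–0.5 with MELD, it alone makes the crude ester-HDL test significant in about 14–71% of studies of 100 patients. Under the paired assumptions for spur cells, the crude test is significant in 7–33%. Adjusting for severity returns both to about 5% when severity is the only common cause. These sizes rest on assumed strengths of relation; the direction rests on the plan's own hypotheses.

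Alcohol aetiology is secondary: it bears on spur cells only, and its effect runs from none to modest depending on the inputs. A reader might infer that the crude tests are invalid or that the primary comparison is compromised. Neither follows: the crude tests describe marginal associations correctly, and the primary comparison of AI groups is a separate analysis. This is a minor improvement to two secondary aims in a self-described pilot.

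**What to change.** For the first two secondary aims, prespecify two results side by side:

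1. The crude association.
2. A MELD-adjusted estimate: linear regression of HDL, and Firth logistic regression of spur cells, each on continuous ester percentage plus MELD.

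State in advance that an association independent of liver disease severity, or a mechanistic role for LCAT, will be claimed only if the adjusted estimate supports it. Otherwise describe the crude result as a marginal association.

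Record alcohol-related aetiology (yes/no) from the chart and add it as a sensitivity covariate, mainly in the spur-cell model.

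The cost is one chart field and two regressions, since MELD is already collected. Intervals will be slightly wider, and few spur-cell events limit how many terms that model can carry, which is the reason for the penalised fit. The simulations above used ordinary logistic regression, so they do not show how the Firth version performs.
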